3.7 Protocol Deviations

Not applicable.

3.8 Key Data Items

Study Analysis Population Definition:

- Intended-To-Treat (ITT) population: All subjects who consented into the study and were randomized to use either irrigation product (Irrisept or SoC).

Important Derived Variables:

- Age = (Screening Date – Date of Birth +1)/365.25.
- Concomitant Medication and Treatments: The medications and treatments started after enrolled to the study (date of Informed Consent).
- Treatment emergent AE or ADE (TEAE/TEADE): Any AE (ADE) started on or after the day of using study device.

Formulas of Metric Conversion:

- 1 inch = 2.54 cm
- 1 lb = 0.4536 kg
- $^{\circ}\text{C} = ({}^{\circ}\text{F} - 32) \times 5/9$

AE Severity

GRADE	DESCRIPTION
0	No AE (or within normal limits)
1	Mild; asymptomatic or mild symptoms; clinical or diagnostic observations only; intervention not indicated
2	Moderate; minimal, local, or noninvasive intervention indicated; limiting age-appropriate instrumental activities of daily living (ADL)
3	Severe or medically significant but not immediately life-threatening; hospitalization or prolongation of hospitalization indicated; disabling; limiting self-care ADL
4	Life-threatening consequences; urgent intervention indicated
5	Death related to AE

AE Relationship to Study Device

By relationship to study product according to the mapping scheme below:

- Potentially related: including the ratings of "definitely", "probably" or "possibly"
- Unlikely related: including the ratings of "unlikely" or "unrelated"

3.9 Change to Planned Protocol Analysis

Not applicable.

4. OUTPUT PLANNED FOR THE STUDY REPORT

4.1 Tables to be Included in Study Report

4.1.1 *Summary of subject information*

1. Table [TDS01] Subject Disposition – ITT population
2. Table [TSC01] Summary of Surgical Procedure by Device Group – ITT Population
3. Table [TDM01] Summary of Demographics – ITT Population
4. Table [TDA01] Summary of Study Device Deficiencies – ITT Population

4.1.2 *Summary of AE*

5. Table [TAE01] Number (%) of Subjects with Adverse Events by MedDRA System Organ Class, High Level Group Term, High Level Term and Preferred Term – ITT Population
6. Table [TAE02] Number (%) of Subjects with Serious Adverse Events by MedDRA System Organ Class, High Level Group Term, High Level Term and Preferred Term – ITT Population
7. Table [TAE03a] Number (%) of Subjects with Adverse Events Grade 2 or Less by MedDRA System Organ Class, High Level Group Term, High Level Term and Preferred Term – ITT Population
8. Table [TAE03b] Number (%) of Subjects with Adverse Events Grade 3 or Higher by MedDRA System Organ Class, High Level Group Term, High Level Term and Preferred Term – ITT Population
9. Table [TAE04] Number (%) of Subjects with Adverse Events Potentially Related to Study Device by MedDRA System Organ Class, High Level Group Term, High Level Term and Preferred Term – ITT Population
10. Table [TAE05] Number (%) of Subjects with Adverse Events by Preferred Term and Overall Frequency – ITT Population
11. Table [TAE06] Number (%) of Subjects with Serious Adverse Events by SAE Criteria – ITT Population
12. Table [TAE07] Number (%) of Subjects with Adverse Events by Onset Time and Outcome – ITT Population
13. Table [TAE08] Number (%) of Subjects with Adverse Events by Severity and Relationship to Study Device – ITT Population
14. Table [TAE09] Number (%) of Subjects with Adverse Events by Action Taken and Irrisep Device Use Information – ITT Population

4.1.3 *Summary of ADE*

15. Table [TADE01] Number (%) of Subjects with Adverse Device Effects by MedDRA System Organ Class, High Level Group Term, High Level Term and Preferred Term – ITT Population
16. Table [TADE02] Number (%) of Subjects with Serious Adverse Device Effects by MedDRA System Organ Class, High Level Group Term, High Level Term and Preferred Term – ITT Population
17. Table [TADE03] Number (%) of Subjects with Unanticipated Serious Adverse Device Effects by MedDRA System Organ Class, High Level Group Term, High Level Term and Preferred Term – ITT Population
18. Table [TADE04] Number (%) of Subjects with Adverse Device Effects by Preferred Term and Overall Frequency – ITT Population

19. Table [TADE05] Number (%) of Subjects with Serious Adverse Device Effects by SADE Criteria – ITT Population

4.2 Listings to be Included in the Clinical Study Report

4.2.1 *Listings of subject information*

1. Listing [LDS01] Discontinued Subjects – ITT Population
2. Listing [LSC01] Surgical Procedure Information – ITT Population
3. Listing [LDM01] Demographic Characteristics – ITT Population
4. Listing [LMH01] General Medical History – ITT Population
5. Listing [LMH02] Allergy History – ITT Population
6. Listing [LCM01] Concomitant Medications and Therapies – ITT Population
7. Listing [LPD01] Study Product (Irrisept Device) Deficiency – ITT Population
8. Listing [LPD02] Study Product (SoC Device) Deficiency – ITT Population

4.2.2 *Listings of AE*

9. Listing [LAE01a] Adverse Events (Irrisept Device Group) – ITT Population
10. Listing [LAE02a] Serious Adverse Events (Irrisept Device Group) – ITT Population
11. Listing [LAE03a] Adverse Events Grade 2 or Less (Irrisept Device Group) – ITT Population
12. Listing [LAE04a] Adverse Events Grade 3 or Higher (Irrisept Device Group) – ITT Population
13. Listing [LAE05a] Adverse Events Potentially Related to Study Device (Irrisept Device Group) – ITT Population
14. Listing [LAE06a] Adverse Events Result Death (Irrisept Device Group) – ITT Population
15. Listing [LAE01b] Adverse Events (SoC Device Group) – ITT Population
16. Listing [LAE02b] Serious Adverse Events (SoC Device Group) – ITT Population
17. Listing [LAE03b] Adverse Events Grade 2 or Less (SoC Device Group) – ITT Population
18. Listing [LAE04b] Adverse Events Grade 3 or Higher (SoC Device Group) – ITT Population
19. Listing [LAE05b] Adverse Events Potentially Related to Study Device (SoC Device Group) – ITT Population
20. Listing [LAE06b] Adverse Events Result Death (SoC Device Group) – ITT Population

4.2.3 *Listings of AED*

21. Listing [LADE01a] Adverse Device Events (Irrisept Device Group) – ITT Population
22. Listing [LADE02a] Serious Adverse Device Events (Irrisept Device Group) – ITT Population
23. Listing [LADE03a] Unanticipated Serious Adverse Device Events (Irrisept Device Group) – ITT Population
24. Listing [LADE01b] Adverse Device Events (SoC Device Group) – ITT Population
25. Listing [LADE02b] Serious Adverse Device Events (SoC Device Group) – ITT Population
26. Listing [LADE03b] Unanticipated Serious Adverse Device Events (SoC Device Group) – ITT Population

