 - Investigator's medical opinion of likely cause of the event and device relationship
 - Description of device use during closed study, including any problems with the device or actions taken with the device as a result of the adverse event
- For subjects who have a device deficiency related to Irrisept identified in the Source records:
 - Dates of report and verification Irrisept was used for irrigation in closed study
 - Description and nature of deficiency
 - Documentation of whether the deficiency was related to any adverse event
 - Investigator's opinion if the deficiency could result in an adverse event if it were to recur

The Investigator or designee is responsible for completing, in a timely manner, an eCRF for each subject and all eCRFs for previously reported or newly detected AEs and device deficiencies. The Investigator or designee is responsible for reviewing completed eCRFs to attest that all data entered are complete and accurate after the monitor finishes the source document verification process. The Investigator is responsible for reviewing and signing each eCRF to indicate the Investigator has thoroughly inspected data and certifies its completeness and accuracy.

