An SADE is an adverse event related to the presence or performance of the device or any component of the system that results in one of the following outcomes:

- Requires hospitalization;
- Prolongs hospitalization;

- Life-threatening;
- Results in congenital anomaly/birth defect;
- Results in death.
- The SAE defined above is also apply to SADE.

Unanticipated Serious Adverse Device Effect (USADE)

A USADE is any serious adverse effect on:

- Health or Safety;
- Any life-threatening problem or death caused by, or associated with, a device, if that effect, problem, or death was not previously identified in nature, severity, or degree of incidence in the investigational plan or application;
- Any other unanticipated serious problem associated with a device that related to the rights, safety, or welfare of subject.

An unanticipated serious adverse device effect is an effect by which its nature, incidence, severity or outcome has not been identified in the risk analysis report.

Device Deficiency

A Device Deficiency is any inadequacy of a medical device with respect to its identity, quality, durability, reliability, safety and performance. Device deficiencies include malfunctions, use errors and inadequate labelling. A device deficiency does not need to relate to an adverse event.

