2.2.2 Anticipated Adverse Device Effects Associated with Use of Irrisept

Table 1 lists the potential risks associated with use of Irrisept based on the product risk analysis and the potential adverse device effects that are anticipated with these risks. Potentially serious adverse device effects (anticipated SADE) have been assessed as a lower probability of occurrence.

TABLE 1: POTENTIAL RISKS AND ANTICIPATED ADVERSE DEVICE EFFECTS FOR IRRISEPT

Potential Risk	Risk Assessment and Risk Mitigations	Potential Anticipated Effects
Allergic or anaphylactic response to CHG	Potential for allergic reaction 
 Potential allergy to CHG is known to occur with other products containing CHG. However, serious allergic reaction is rare based on data published by the U.S. FDA on topical skin products containing CHG.1 Product is labeled as do not use in patients with CHG allergy. A known CHG allergy was an exclusion criterion in the closed study protocol. 	ADE: Minor non-serious allergic reaction (e.g., rash, dermatitis, itching, rhinitis) SADE: Serious or life-threatening allergic reaction requiring medical intervention (e.g., shortness of breath, tachycardia, tightness in throat, dizziness, anaphylactic reaction)
Exposure to bio-incompatible material or chemical with potential for adverse tissue reaction	Potential for toxicity reaction 
 Patient contact materials have passed biocompatibility testing per ISO standard 10993-1. Manufacturing process validations and quality control procedures have been completed to ensure product integrity and quality. 	ADE: Minor tissue irritation, as manifested by symptoms such as pain, erythema, edema, itching, burning SADE: Severe adverse tissue reaction that requires or prolongs hospitalization, or requires medical or surgical intervention to prevent permanent impairment

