3. STATISTICAL METHODS

3.1 General

All data will be analyzed using the Statistical Analysis System (SAS®; Version 9.2 or higher).

Safety data will be summarized by study device group in summary tables. Continuous variables will be presented by descriptive statistics: n, mean, standard deviation (SD), median, minimum, and maximum, and categorical variables will be tabulated by frequency count and percentage.

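### The SAP reports unanticipated serious device effects for the SoC group, but neither document defines what is anticipated for SoC, so the between-group contrast cannot be interpreted

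*SAP*

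**What the plan says.** **USADE outputs.** SAP 4.1.3 plans TADE03, "Number (%) of Subjects with Unanticipated Serious Adverse Device Effects", on the ITT population. Its title names no groups, but SAP 3.1 states that "Safety data will be summarized by study device group in summary tables", so an SoC column follows. SAP 4.2.3 adds a separate SoC listing, LADE03b: "Unanticipated Serious Adverse Device Events (SoC Device Group").

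**What counts as anticipated.** SAP 2.2.1 and Protocol 7.1.5 make an effect unanticipated when the risk analysis report does not identify it. Protocol 7.1.5 points to the section that follows for that report, and that section contains Table 1. SAP 2.2.2 gives its scope: "Table 1 lists the potential risks associated with use of Irrisept based on the product risk analysis". There is no SoC entry.

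**How USADE is worded.** Protocol 7.1.5 defines the term in one sentence with a condition that the effect was not identified beforehand. SAP 2.2.1 opens with "A USADE is any serious adverse effect on" and breaks the rest into bullets.

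**Deficiencies.** SAP 4.2.1 plans LPD02, "Study Product (SoC Device) Deficiency", and SAP 4.1.1 plans a deficiency table, TDA01, on ITT. The detail fields in Protocol 9.1 are headed "For subjects who have a device deficiency related to Irrisept identified in the Source records".

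**The concern.** Table 1 already names severe infection, wound dehiscence, non-healing wound, adverse tissue reaction and serious allergy as anticipated for Irrisept. These are also serious events one would look for after an open laparotomy with any irrigation. If only Irrisept has a list, the label *unanticipated* depends on which product was used as well as on what happened to the patient. Protocol 9.2 leaves the Medical Monitor unblinded, so the group is known when the call is made.

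The Protocol summary frames the safety endpoint as a comparison of Irrisept with SoC, and the results go into a final study report and the product risk assessment. A USADE table with two columns invites a comparison in which one column has no reference standard. The deficiency outputs raise a similar question, because the protocol is not consistent about whether SoC deficiencies are within its scope.

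**Working it through.** The documents give no rate, margin or sample size for these outputs, so there is no planned figure to reproduce. The check traces each SoC output back to its classification rule and its data field.

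**Step 1: can an SoC USADE arise?** Yes. Protocol 7.2.3 lets an event be rated as related to the SoC. Protocol 7.2.1 has the Investigator and the Medical Monitor each call a device effect anticipated or unanticipated. Protocol 2.2 left the choice of SoC to each investigator or institution, so there is no single SoC product from which a list could be inferred.

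**Step 2: the value of the SoC cell.** Let *s* be the number of SoC subjects with a SADE.

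- Reading A (literal): Table 1 has no SoC entries, so all are unanticipated and the cell is *s*, the same as in TADE02.
- Reading B: the device in the USADE definition means Irrisept only, so the cell is 0.
- Reading C: the adjudicator uses judgment, the closed-study plan, or Table 1 by analogy, so the cell lies between 0 and *s*.

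Protocol 2.1 gives 600 randomized 1:1, and 600/2 = 300. Using 300 as the SoC denominator is an assumption, because Protocol 8.3 groups by product actually used and those counts are not given.

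| *s* | Reading A | Reading B | Reading C |
|---|---|---|---|
| 1 | 1/300 = 0.33% | 0% | 0% to 0.33% |
| 3 | 3/300 = 1.00% | 0% | 0% to 1.00% |
| 5 | 5/300 = 1.67% | 0% | 0% to 1.67% |
| 10 | 10/300 = 3.33% | 0% | 0% to 3.33% |

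**Step 3: the contrast if the products were equally safe.** Suppose *s* subjects in each group have a SADE and *a* of those in the Irrisept group have only Table 1 events, none made unanticipated by its severity or frequency. The Irrisept cell is *s* − *a*.

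- Reading A: SoC minus Irrisept = *s* − (*s* − *a*) = *a*. With *s* = *a* = 5, the table shows 0/300 (0%) for Irrisept and 5/300 (1.67%) for SoC.
- Reading B: SoC minus Irrisept = 0 − (*s* − *a*) = −(*s* − *a*), which is zero or against Irrisept.

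The sign of the contrast therefore depends on a rule that is not written.

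**Step 4: the definition.** In the Protocol 7.1.5 sentence, the not-previously-identified condition governs the effect on health or safety as well as life-threatening problems and death. In SAP 2.2.1, the health-or-safety bullet stands alone and only the second bullet carries the condition. Taken by itself, the first bullet admits any serious adverse effect on health. The sentence after the bullets requires that the risk analysis report has not identified the effect. The two conflict, and SAP 3.9 declares no change from the protocol.

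**Step 5: deficiencies side by side.**

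- Irrisept only: the scope statement in Protocol 7 and the detail fields in Protocol 9.1.
- Not limited to Irrisept: the all-subject deficiency check and the eCRF entry rule in Protocol 9.1, the review of all subjects' records in Protocol 9.2, the general definition in Protocol 7.1.8, and SAP 3.5.

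An SoC deficiency can thus be entered, but no detail fields are specified for LPD02 to list. Grouping by product used adds a further gap. Table 1 names saline as available when an Irrisept bottle cannot be used, so an Irrisept deficiency could occur in a subject analyzed as SoC, although the detail fields ask for confirmation that Irrisept was used.

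**The case against.** The best reply is that classification is a clinical judgment made event by event under Protocol 7.2.1, not a mechanical look-up in Table 1. The definition also refers to the investigational plan or application, and the closed-study documents are not available here. The outputs are counts and percentages with no test. The Sponsor's own assessment under Protocol 7.2.1 concerns effects related to Irrisept, and TADE01 and TADE02 already compare groups without needing an anticipated list.

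Most of this stands, and it rules out some stronger readings. A reader might infer that the SoC USADE cell is fixed in advance, or that the contrast must favour Irrisept. Neither follows: Reading A favours Irrisept, Reading B does not, and the documents do not choose. A reader might also infer that SoC deficiencies must read zero. The all-subject check and the unrestricted eCRF entry in Protocol 9.1 contradict that. A p-value for such a contrast would describe a test that the plan does not contain.

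On the bullets, it is fair to say that the sentence after them restores the condition and that the SAP only tabulates calls made elsewhere. No changed result has been shown.

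What the reply does not supply is a rule for SoC. Judgment without a reference list, made with the group known, leaves the SoC column without a defined meaning.

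**Conclusion.** The SoC part of the USADE reporting is undefined. On the same data the SoC cell can run from 0 to every SoC SADE, for example 0% to 1.67% with 5 such subjects among an assumed 300. The contrast in TADE03 is therefore uninterpretable. Under the literal rule it favours Irrisept by the number of subjects whose SADEs fall within Table 1.

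The consequence is limited. These are descriptive outputs, and the Irrisept USADE counts do not depend on how SoC is classified. The bulleted definition is a drafting error that should be corrected because it contradicts both the protocol and the SAP's own next sentence. For deficiencies, the supported finding is an inconsistency over scope and missing detail fields for SoC. The documents do not establish an absence of SoC data or a bias in a known direction.

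The conclusion rests on the two documents supplied. A reference list for SoC in the closed-study plan, if one exists, would change it.

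**What to change.** 1. Restrict TADE03 and the LADE03 listings to Irrisept-treated subjects and delete LADE03b. Leave the between-group comparison of serious device effects on TADE02, which is already planned. For that table, state that an SoC device effect is one rated as related to the SoC irrigation, as Protocol 7.2.3 allows. The cost is that there is no SoC USADE column.
2. Replace the USADE bullets in SAP 2.2.1 with the Protocol 7.1.5 sentence, unchanged.
3. Reconcile Protocol 7 and the Irrisept-only detail fields in Protocol 9.1 with the all-subject check and eCRF entry in Protocol 9.1 and 9.2, and with LPD02 and TDA01 in the SAP. Say whether SoC deficiencies are in scope, which fields they carry, and where an Irrisept deficiency is counted when the subject is analyzed as SoC. Until then, do not present SoC deficiency counts as a comparison with Irrisept. Do not discard SoC deficiency records that have been entered or label them as not collected.

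Items 1 and 2 need only SAP wording and no new data. Item 3 needs a clarification in both documents.
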